## **7.3 TREATMENT COMPLIANCE**

### **7.3.1 CRF Compliance**

Only descriptive statistics are planned for this section of the report. Treatment compliance is calculated at Week 1, 2, 4, 6, 8, 10 and 12(EOT) based on the CTP's flow chart.

Treatment Compliance = (number of tablets taken during a period) / (number of tablets that should have been taken during a period) \* 100.

The cumulative treatment compliance during the entire treatment period is derived using the following examples:

For completers: if a subject's observed treatment compliance rates are 80%, 81%, 82%, 83%, 84%, 85%, 86% at Weeks 1, 2, 4, 6, 8, 10 and 12, then the cumulative treatment compliance percent =  $(.80*1 + .81*1 + .82*2 + .83*2 + .84*2 + .85*2 + .86*2)/12*100 = 83.42\%$ .

For early discontinued subject: if a subject's observed treatment compliance rates are 80% at Week 1, 81% at Week 2, 82% at Week 4, 50% at eEOT, then the cumulative treatment compliance rate =  $(0.80*1 + 0.81*1 + 0.82*2 + 0.5*((eEOT\ date - drug\ start\ date + 1)/7 - 4))/((eEOT\ date - drug\ start\ date + 1)/7) * 100\% = 74.3\%$  if the quantity (eEOT date – drug start date + 1) is assumed to be 36 days.

If at a particular visit a participant did not return the trial drug kits, then the compliance at that visit is zero.

Treatment compliance will be summarised overall and by visit for the treated set (FAS) using descriptive statistics (N, mean, SD, minimum, median, maximum). The number and percentage of patients with the following overall compliance categories will be presented

using descriptive statistics (N, mean, SD, minimum, median, maximum). The number and percentage of patients with the following overall compliance categories will be presented:

- "<80%",
- "80% to <100%",
- "≥100%",
- missing.

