
Proprietary confidential information © 2022 Boehringer Ingelheim International GmbH or one or more of its affiliated companies

Trial Periods	Screening		Treatment													Early D/C	Follow-up		End of Trial
	1 	1A	2	3	4	4A ☎	5	5A ☎	6	6A ☎	7	7A ☎	8	8A ☎	9 EoT 		eEOT 	FUP1	
Visit	1 	1A	2	3	4	4A ☎	5	5A ☎	6	6A ☎	7	7A ☎	8	8A ☎	9 EoT 	eEOT 	FUP1	FUP2 ☎	EoTrial
Week	-4 to -1			1	2	3	4	5	6	7	8	9	10	11	12		13	14	16
Day	-28 to -7	-5	1 	8	15	22	29	36	43	50	57	64	71	78	85		EoT +7	EoT +14	EoT +28
Time window for visits (in days)	-28 to -7	-7 to -5	V1 + 7 to 28	±2	±2	±2	±2	±2	±2	±2	±2	±2	±2	±2	±2		±2	±2	±2
ZAN-BPD 	X		X 	X	X		X	X		X		X		X	X	X			
CGI-S 			X	X	X		X	X		X		X		X	X	X			
C-SSRS 	X	X	X 	X	X	X	X	X	X	X	X	X	X	X	X	X	X	X	X
DERS-16 	X		X	X	X		X	X		X		X		X	X	X			
STAI-S 	X		X	X	X		X	X		X		X		X	X	X			
PHQ-9 	X		X	X	X		X	X		X		X		X	X	X			
██████████			█										█		█	█			
PGI-S 			X	X	X		X	X		X		X		X	X	X			
██████████			█	█	█		█	█		█		█		█	█	█			
██████████			█											█	█	█			
██████████			█					█						█	█	█			
██████████	█	█											█	█	█	█			
██████████		█																	
All AEs/SAEs/AESIs 	X	X	X	X	X	X	X	X	X	X	X	X	X	X	X	X	X	X	X
Compliance check 				X	X		X		X		X		X		X	X			
Concomitant therapy	X	X	X	X	X	X	X	X	X	X	X	X	X	X	X	X	X	X	X

Trial Periods	Screening		Treatment													Early D/C	Follow-up		End of Trial
	1 	1A	2	3	4	4A	5	5A	6	6A	7	7A	8	8A	9		eEOT 	FUP1	
Visit															EoT 				
Week	-4 to -1			1	2	3	4	5	6	7	8	9	10	11	12		13	14	16
Day	-28 to -7	-5	1 	8	15	22	29	36	43	50	57	64	71	78	85		EoT +7	EoT +14	EoT +28
Time window for visits (in days)	-28 to -7	-7 to -5	V1 + 7 to 28	±2	±2	±2	±2	±2	±2	±2	±2	±2	±2	±2	±2		±2	±2	±2
Termination of trial medication															X 	X			
Completion of patient participation																			X

Phone visit

- 1 Visit 1 procedures are not required to be completed on the same day.
- 2 For patients who permanently discontinue trial drug prior to the scheduled Week 12 EoT visit, the Early EoT (eEoT) visit must be completed as soon as possible after trial drug discontinuation. See section 6.2.3 for further details regarding patient follow-up after premature treatment discontinuation.

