#### 4.3 TREATMENT COMPLIANCE

Patients are required to bring all trial medication, including empty package materials, with them to each visit.

Treatment compliance will be calculated based on tablet count, as shown in the formula below. Compliance will be verified by the Clinical Research Associate (CRA) by using the returned-tablet count that is recorded in the source documents.

$$\text{Treatment compliance (\%)} = \frac{\text{Number of tablets taken} \times 100}{\text{Number of tablets which should have been taken (as directed by the investigator)}}$$

The potential for abuse of trial medication should be closely monitored. Site staff should discuss and thoroughly document the reasons for compliance that is less than 80% or greater than 100% and events of overdose, misuse, lost and unaccounted medication in the participant's source, and on the appropriate eCRFs.

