#### Patients prematurely discontinuing study drug

If the trial drug intake needs to be permanently stopped for any reason prior to the scheduled Week 12 visit, the eEoT visit will be completed instead of the planned treatment period visit as soon as possible after trial drug discontinuation. See section 6.2.3 below for further details regarding patient follow-up after premature treatment discontinuation.

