### 7.3.2 AiCure Adherence

First, we define overall AiCure Adherence (abbreviated as OAA), as the sum of all tablet adherence minus the total number of tablets flagged as red, orange, or yellow alerts, divided by a denominator of 4 times 84. Or, in other words:

- $OAA = \frac{[(\text{Sum of all tablet adherence}) - (\text{total number of red, orange, and yellow alerts})]}{4 \times 84} \times 100$ ,
  - o 84 = Number of days on treatment, and 4 is the number of tablets per dose.

Tablet adherence is the successful administration of a pill as captured by AiCure video. *Red alerts* are tablet administrations for which the AiCure video captures the dosing process, but includes strong visual proof of deceptive behaviors, non-adherence, and/or overdose of study drug. Examples include removing study drug from the mouth, ‘cheeking’, spitting out the drug, or using non-IP to dose. Also, in cases for which more than one pill was ingested simultaneously, a red alert is flagged. For *orange alerts*, the video captures the dosing process, but contains suggested visual proof of potentially deceptive behavior, potential non-adherence, or shows potential overdose of study drug. And lastly, for *yellow alerts* the video is missing visual information necessary to confirm adherence.

Note that tablet adherence is the administration of a tablet by the following method: visually confirmed by the AiCure app.

For subjects that discontinue treatment early, 84, which is the number of days from randomization to the planned treatment end, will be replaced by the total number of days from randomization to the respective date of early treatment discontinuation.

As defined in [Section 6.3](#), the Adherent set (AS) consists of all subjects in FAS that achieved an OAA of at least 60%. Within these subjects, flags (or classifications) will be built to denote increasing thresholds of adherence ( $\geq 60\%$ ,  $\geq 75\%$ ,  $\geq 90\%$ ). Hence, it may be of interest to evaluate the effect of varying levels of overall adherence on efficacy.

An evaluation of the primary endpoint to varying levels of adherence to treatment may be of interest, please see [Section 7.4.2.3](#) for further details.

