## **7.7 EXTENT OF EXPOSURE**

Extent of exposure will be calculated as the difference between last intake of study drug and the first administration of the study drug plus one day. Descriptive statistics will be provided for number of days of exposure for each treatment arm. Also, cumulative exposure of number and percentage (N, %) of subjects will also be displayed as “< 1 week”, “1 to < 2 weeks”, “2 to <3 weeks”, “3 to <4 weeks”, “4 to <6 weeks”, “6 to <8 weeks”, “8 to <10 weeks”, “10 to <12 weeks”, “12 weeks”, “>12 weeks”, or “missing”.

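### Cumulative compliance of early discontinuers runs to the eEOT visit rather than to the last dose, which over-weights the last-period rate

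*SAP*

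**What the plan says.** SAP 7.3.1 defines compliance within a period as "number of tablets taken during a period) / (number of tablets that should have been taken during a period", times 100. It then shows by example how the period rates are combined into a cumulative figure.

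- **Completer:** the seven period rates are weighted 1, 1, 2, 2, 2, 2 and 2 weeks and divided by 12, giving 83.42%.
- **Early discontinuer:** the rates are "80% at Week 1, 81% at Week 2, 82% at Week 4, 50% at eEOT". The first three get weights of 1, 1 and 2 weeks. The last gets the time from drug start to the eEOT date, in weeks, minus 4. The divisor is that same total time. The SAP states 74.3% "if the quantity (eEOT date – drug start date + 1) is assumed to be 36 days".

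The section also scores a visit as zero if the drug kits are not returned. The results are tabulated with a category limit at 80%.

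The eEOT is a visit, and it follows the end of dosing. Flow Chart footnote 2 says "the Early EoT (eEoT) visit must be completed as soon as possible after trial drug discontinuation", and Protocol 6.2.2 says "the eEoT visit will be completed instead of the planned treatment period visit as soon as possible after trial drug discontinuation". SAP Table 6.7: 1 describes it by reference to the last administration plus 7 days.

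Two other SAP rules end earlier. For AiCure adherence in early discontinuers, the 84 days "will be replaced by the total number of days from randomization to the respective date of early treatment discontinuation". SAP 7.7, counting in days, says "Extent of exposure will be calculated as the difference between last intake of study drug and the first administration of the study drug plus one".

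**The concern.** No tablet is due once the drug has been stopped, yet the days between the last dose and the eEOT visit, and the visit day itself, enter the cumulative figure as treatment time. The same patient therefore has one dosing period for tablet-count compliance and a shorter one for AiCure adherence and exposure.

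The completer rule does not share the problem. Its 12 weeks are 84 days, and Protocol 6.2.2 puts the last dose on the day before the EoT visit, which is scheduled for Day 85. The earlier checks behave the same way: Weeks 1, 2 and 4 fall on Days 8, 15 and 29 and carry cumulative weights of 7, 14 and 28 days, so the visit day is not counted. Only the eEOT term adds it.

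At stake is a descriptive table by arm. The rule applies only to discontinuers, so arms with different discontinuation patterns are not summarised on quite the same basis.

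**Working it through.** **Inputs.** Period rates and the 36 days come from SAP 7.3.1. The gap g between last dose and eEOT visit is not fixed by the protocol. I take 1 to 7 days as an assumption, with 7 from SAP Table 6.7: 1.

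**Formula.** With r the last-period rate and D the days counted:

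C(D) = (0.80×1 + 0.81×1 + 0.82×2 + r×(D/7 − 4)) / (D/7) = (3.25 + r×(D/7 − 4)) / (D/7)

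The mean over Weeks 1 to 4 is 3.25/4 = 81.25%.

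**1. The SAP's own figures.**
- Completer: 10.01/12 = 83.42%, as stated.
- Discontinuer, r = 0.50, D = 36: (3.25 + 0.5×1.143)/5.143 = 74.3%, as stated.

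**2. Same example, ended at the last dose (D = 36 − g, 50% rate kept).**
- g = 1: 75.0%
- g = 2: 75.7%
- g = 4: 77.3%
- g = 7: 80.2%, which leaves the lowest category (below 80%)

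**3. Dependence on the last-period rate.** D appears in the numerator as well as in the divisor, so C(D) is a weighted mean.
- r = 50%: 74.3% to the visit, 80.2% to the last dose at g = 7. The visit date lowers the figure.
- r = 81.25%: 81.25% for every D. No effect.
- r = 100%: 85.4% to the visit, 81.9% to the last dose at g = 7. The visit date raises the figure.
- All periods at 100%: (4 + (D/7 − 4))/(D/7) = 100% for every D.

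**4. Unreturned kit.** The eEoT is a kit-return visit (Protocol 4.1.4), and an unreturned kit scores zero. With r = 0 the numerator is 3.25 weeks = 22.75 days:
- to the visit: 22.75/36 = 63.2%
- to the last dose at g = 7: 22.75/29 = 78.4%

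**5. The period rate itself.** Neither document says on what date tablets due stop accruing in the last period. If they ran to the visit, a patient who took every tablet until stopping would score (36 − g)/36, which is 97.2% at g = 1 and 80.6% at g = 7, instead of 100%. This step is conditional on that reading.

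**The case against.** A reader might infer that the rule makes discontinuers in general look less compliant than they were, and so could mimic dose-related non-adherence. The documents do not support that. Step 3 shows that the formula only re-weights the last period: a patient who took drug as directed until stopping stays at 100%. A consistent downward bias needs tablets to remain due after the drug is stopped. Neither document says so, and the protocol's denominator, "Number of tablets which should have been taken (as directed by the investigator"), reads more naturally the other way.

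The remaining objections bear on size and wording.

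- **The category crossing is an edge case.** It needs the full 7-day gap although the visit is to be as soon as possible. With D = 29 the last period is a single day, so 50% means 2 of 4 tablets. At a 1-day gap the shift is 0.7 points. This stands.
- **The completer divisor is nominal.** It coincides with a last dose on Day 84 but is not stated as a last-dose rule. This also stands, so SAP 7.3.2 and 7.7 are the firmer comparison.
- **Few patients may be affected.** The planned 20% dropout is 0.20 × 355 = 71 patients, but this is at most a rough ceiling. Those with equal period rates, or with only one period, are unaffected.
- **Swapping the date alone creates a new problem.** A patient dosed at a Week 4 visit on Day 27, inside the ±2-day window, who then takes nothing more would get a last-period weight of 27/7 − 4 = −0.14 weeks. This is correct, and the fix has to deal with it.

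None of these removes the inconsistency in the end date.

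**Conclusion.** The rule is wrong as written, and the point is minor. Off-drug days count as treatment time, contrary to SAP 7.3.2 and 7.7 and out of line with the 84-day basis for completers. The cumulative figure is distorted whenever the last-period rate differs from the earlier mean, and the sign follows that difference.

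In the SAP's example the understatement is 0.7 points at a 1-day gap and 5.9 points at 7 days (80.2 − 74.3). With an unreturned kit it is 15.2 points at 7 days (78.4 − 63.2). These sizes rest on the assumed gap and on keeping the last-period rate unchanged when the period is shortened.

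The consequence is limited. SAP 7.3.1 plans only descriptive statistics, and the Adherent Set is built on AiCure adherence, which already ends at discontinuation. The primary analysis is not affected. What can change is an individual patient's side of the 80% limit, and with it the category counts by arm.

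**What to change.** In SAP 7.3.1:

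1. Replace the eEOT date by the date of last intake of trial medication in both places where it appears, the last-period weight and the divisor.
2. State that tablets due in the last period end on that date.
3. Set the last-period weight to no less than zero and divide by the sum of the weights actually used, or use actual visit dates for the earlier periods. The divisor matters: in the Day 27 case, a zero weight with the divisor left at 27 days gives 22.75/27 = 84.3%, whereas the sum of the weights (28 days) gives 81.25%.
4. Recompute the worked example with a stated last-intake date.

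The cost is a few lines of SAP text and a small program change. The last-intake date is already needed for exposure under SAP 7.7, so no new data are required.

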### 7.3.2 AiCure Adherence

First, we define overall AiCure Adherence (abbreviated as OAA), as the sum of all tablet adherence minus the total number of tablets flagged as red, orange, or yellow alerts, divided by a denominator of 4 times 84. Or, in other words:

- $OAA = \frac{[(\text{Sum of all tablet adherence}) - (\text{total number of red, orange, and yellow alerts})]}{4 \times 84} \times 100$ ,
  - o 84 = Number of days on treatment, and 4 is the number of tablets per dose.

Tablet adherence is the successful administration of a pill as captured by AiCure video. *Red alerts* are tablet administrations for which the AiCure video captures the dosing process, but includes strong visual proof of deceptive behaviors, non-adherence, and/or overdose of study drug. Examples include removing study drug from the mouth, ‘cheeking’, spitting out the drug, or using non-IP to dose. Also, in cases for which more than one pill was ingested simultaneously, a red alert is flagged. For *orange alerts*, the video captures the dosing process, but contains suggested visual proof of potentially deceptive behavior, potential non-adherence, or shows potential overdose of study drug. And lastly, for *yellow alerts* the video is missing visual information necessary to confirm adherence.

Note that tablet adherence is the administration of a tablet by the following method: visually confirmed by the AiCure app.

For subjects that discontinue treatment early, 84, which is the number of days from randomization to the planned treatment end, will be replaced by the total number of days from randomization to the respective date of early treatment discontinuation.

As defined in [Section 6.3](#), the Adherent set (AS) consists of all subjects in FAS that achieved an OAA of at least 60%. Within these subjects, flags (or classifications) will be built to denote increasing thresholds of adherence ( $\geq 60\%$ ,  $\geq 75\%$ ,  $\geq 90\%$ ). Hence, it may be of interest to evaluate the effect of varying levels of overall adherence on efficacy.

An evaluation of the primary endpoint to varying levels of adherence to treatment may be of interest, please see [Section 7.4.2.3](#) for further details.

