### 4.1.4 Drug assignment and administration of doses for each patient

The medication assignment will be provided through IRT. The assigned medication numbers must be entered in the eCRF, and the corresponding medication kits must be given to the patient.

At Visit 2, after randomization, patients will receive their first medication kit. The first dose of trial medication will be taken at the study site under supervision of the investigator or site staff. At each dispensing visit (Visits 2, 5, and 7), patients will receive one medication kit containing supplies for a total of 35 treatment days (28 treatment days plus 7 days reserve). Return of the used/unused medication kits will occur at Visit 5, 7 and EoT/eEoT.

Patients should be instructed not to take their trial medication in the morning of Visits 3, 4, 5, 6, 7 and 8, as patients will be dosed at the site after pre-dose PK sampling. Patients should also be instructed not to take their trial medication in the morning of EoT visit, as a trough PK sample will be taken at that visit (approximately 24 hours after the last dose). For patients that complete the treatment period, the last dose of trial medication should be taken on the

day before the EoT visit. Patients who fail to do so should have the visit rescheduled as soon as possible, ideally on the following day.

Each dose will consist of 4 tablets (Table 4.1.5.1: 1). Patients should be instructed to take the study medication orally with water and with or without food, every morning at approximately the same time. It is recommended that patients continue to take study medication in a consistent way, i.e. either with or without food. If a morning dose is missed by more than 12 hours, that dose should be skipped and the next dose should be taken as scheduled. On days prior to a visit, the morning dose should be taken approximately 24 hours before the planned dose at the visit.

During the COVID-19 pandemic, there may be instances that will prevent a patient from going to the site for a study visit. If the investigator concludes that it is acceptable and safe for the patient to continue trial medication, it is permissible for the trial medication to be shipped from the site to the patient (for more details see section [6.2](#) and [10.3](#)).

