#### Visit 9 / End of Treatment (EoT) Visit

For patients completing the 12-week treatment, this visit will be EoT visit. For patients who discontinue study treatment prematurely and continue with study visits, this visit will be Visit 9 when they reach Week 12.

EoT visit represents the end of the treatment period. Last study drug administration will be on the day before EoT visit. The overall duration of the anticipated treatment period

(Randomization to EoT) should not be less than 83 days; therefore, the EoT visit is scheduled at Day 85 with a visit window of up to  $\pm 2$  days.

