## **5. ENDPOINTS(S)**

### **5.1 PRIMARY ENDPOINT**

Change from baseline in ZAN-BPD total score at Week 10 is the primary efficacy endpoint. See CTP Section 5.1 for details.

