#### MMRM analysis

The change from baseline in ZAN-BPD at Week 10 for each dose group as well as the corresponding variance-covariance matrix are estimated by a mixed effects model repeated measure (MMRM) including the fixed categorical covariates of treatment, visit and the baseline ZAN-BPD total score strata indicator ( $\leq 18$  vs.  $\geq 19$ ), the continuous fixed covariate of baseline ZAN-BPD total score, and treatment-by-visit interaction, as well as baseline-by-visit interaction. Patient is considered as random. The unstructured covariance matrix is used to estimate the within subject variability. The Kenward-Roger approximation will be used to estimate the denominator degrees of freedom. Analyses will be implemented using SAS 9.4 PROC MIXED.

More specifically, the change in ZAN-BPD from baseline (Visit 2), at Visits 3, 4, 5, 6, 7 and 8 (Weeks 1, 2, 4, 6, 8 and 10) will be evaluated using an MMRM accounting for the following sources of variation: 'treatment', 'visit', 'baseline ZAN-BPD strata indicator' ( $\leq 18$  vs.  $\geq 19$ ),

‘baseline ZAN-BPD’ as a continuous covariate, and the ‘treatment\*visit’ and ‘baseline\*visit’ interaction as fixed effects, as well as the random ‘subject’ effect. The methods described in [Section 10.1](#) will be utilized to resolve model non-convergence.

SAS code for MMRM:

The following SAS code will be used to calculate the MMRM.

```
PROC MIXED DATA=indata cl method=reml;
    CLASS visit trt stratum subject;
    MODEL ept = stratum visit*trt base*visit / ddfm=kr s CL;
    REPEATED visit / subject= subject type=un r rcorr;
    LSMEANS visit*trt / pdiff=all om cl alpha=0.10 slice=visit;
```

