### 7.4.2.3 Subgroup analyses to the primary endpoint

The primary efficacy endpoint will be further analyzed for the AiCure adherent subgroup as defined in [Section 6.3](#) and [6.4](#). This study is not adequately powered to confirm treatment differences in any subgroup analysis. Any subgroup analyses performed will be considered exploratory. This subgroup analysis will explore if the treatment effect differs in the AiCure adherent subgroup. The 3 subgroups are: (1) overall adherence  $\geq 60\%$ , (2) overall adherence  $\geq 75\%$ , and (3) overall adherence  $\geq 90\%$ . The conduct of these analyses is subject to the available sample size of the subgroup and more categories could be defined. The same statistical approach and methods used for the primary analysis of the primary efficacy endpoint will be used.

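### AiCure adherence subgroups for the Week 10 endpoint count doses due after Week 10: about one sixth of the score for patients who complete treatment

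*SAP*

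**What the plan says.** SAP 7.3.2 defines overall AiCure adherence as tablets seen to be taken, minus tablets with red, orange or yellow alerts, divided by 4 times 84. It explains the denominator: "84 = Number of days on treatment, and 4 is the number of tablets per dose". The one stated exception is for patients who stop treatment early, for whom the 84 "will be replaced by the total number of days from randomization to the respective date of early treatment discontinuation".

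SAP 6.3 builds the Adherent Set on a score of at least 60%. SAP 7.4.2.3 re-analyses the primary endpoint in patients with at least 60%, 75% and 90% adherence, using the primary methods. Of the purpose it says: "This subgroup analysis will explore if the treatment effect differs in the AiCure adherent subgroup". It calls the analyses exploratory and not adequately powered.

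The endpoint is earlier than the end of the adherence period: "Change from baseline in ZAN-BPD total score at Week 10 is the primary efficacy endpoint". The primary model takes the change "at Visits 3, 4, 5, 6, 7 and 8 (Weeks 1, 2, 4, 6, 8 and 10"), so nothing after Week 10 enters the outcome. SAP Table 6.7:1 plans Visit 8 for Day 71 with a window of Day 69 to Day 75. Dosing continues to about Day 84, since the end-of-treatment visit is planned for Day 85 and "Last study drug administration will be on the day before EoT visit" (Protocol 6.2.2).

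No visible text limits the score to doses before Visit 8.

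**The concern.** Tablets taken after the Week 10 rating cannot change that rating, yet they help decide which adherence group a patient joins. This has two consequences.

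- **Misclassified exposure.** Two patients with the same dosing before the rating can fall on different sides of a threshold because of the last two weeks.
- **Selection after the outcome.** A patient who feels no better at Week 10 may take fewer tablets afterwards. Grouping on that later behaviour can select on response. The documents give no figure for how often this would happen.

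The definition also sits awkwardly with Protocol 3.2, which places the endpoint at Week 10 to avoid effects of perceived abandonment near the end of treatment. The adherence score brings those two weeks back in as a classifier.

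At stake is the reading of a pre-specified exploratory analysis of effect by adherence.

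**Working it through.** **Inputs**
- Four tablets per day: "Each dose will consist of 4 tablets" (Protocol 4.1.4).
- 84 days in the denominator (SAP 7.3.2).
- Rating planned for Day 71, window Day 69 to 75 (SAP Table 6.7:1).
- Thresholds of 60%, 75% and 90% (SAP 7.3.2 and 7.4.2.3).
- Assumptions: one dose due on each of Days 1 to 84, and on-site doses credited by AiCure like home doses.

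**The plan's own figure.** 12 weeks x 7 = 84 days, and Day 85 − 1 = Day 84 for the last dose. 84 x 4 = 336 tablets. The denominator reproduces.

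**Share of the denominator after the outcome, for a completer.** Share = (84 − dosing days before the rating) / 84.

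| Rating day and dose order | Days before | Days after | Share |
|---|---|---|---|
| Day 71, dose after rating | 70 | 14 | 14/84 = 16.7% |
| Day 71, dose before rating | 71 | 13 | 13/84 = 15.5% |
| Day 69, dose after rating | 68 | 16 | 16/84 = 19.0% |
| Day 75, dose after rating | 74 | 10 | 10/84 = 11.9% |

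**Effect on classification** (70 days before, 14 after). Score = (70a + 14b) / 84, where a and b are the credited fractions before and after the rating.

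- a = 55%, b = 100%: (38.5 + 14)/84 = 62.5%. The patient enters the ≥60% group although below 60% when rated.
- a = 95%, b = 50%: (66.5 + 7)/84 = 87.5%. The patient misses the ≥90% group although at 95% when rated.

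**Pre-rating adherence needed to pass threshold t** = (84t − 14b)/70.

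| Threshold | Days needed (84t) | If b = 100% | If b = 0 |
|---|---|---|---|
| 60% | 50.4 | 36.4/70 = 52% | 50.4/70 = 72% |
| 75% | 63.0 | 49.0/70 = 70% | 63.0/70 = 90% |
| 90% | 75.6 | 61.6/70 = 88% | 75.6/70 = 108%, impossible |

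The b = 0 column is a limiting case for a patient scored on 84 days. A patient perfect up to Day 70 and still scored on 336 tablets needs 0.9 x 336 − 280 = 22.4, so 23 further credited tablets, to reach 90%.

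**After the change.** With a Day 71 rating the denominator is 70 x 4 = 280 tablets. The two example patients score 154/280 = 55% and 266/280 = 95%, and each falls on the side of the threshold that matches exposure before the rating.

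**The case against.** The strongest reply is that the consequence is small. SAP 7.4.2.3 calls these analyses exploratory, underpowered and subject to available sample size. The primary analysis uses the full analysis set and does not involve the score. The documents do not allow an estimate of how many patients would be reclassified or how any effect estimate would move. All of this stands.

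Several stronger readings are tempting, but the documents do not support them.

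- **Full adherence before the endpoint can score anywhere from 83% to 100%.** A reader might infer this from a patient who is perfect to Day 70 and then takes nothing: 70/84 = 83.3%, against 70/70 = 100% if recorded as stopping. But the Flow Chart (footnote 2) and Protocol 6.2.2 treat permanent stopping before Week 12 as early discontinuation, so the shorter denominator would normally apply. The 83.3% needs an unrecorded stop, or doses taken but not confirmed on video. Partial skipping is the realistic case.
- **Exactly 14 days always follow the rating.** The documents do not say that the Visit 8 rating precedes that day's dose. Only at Visit 2 is the dose placed after all assessments. The visit window varies the count further.
- **Every patient is affected.** Patients who stop before Visit 8 are scored on days up to their stop, so no post-outcome dose counts.
- **The subgroups fail to answer the SAP's question.** The SAP asks about overall adherence, and a whole-treatment score fits that wording. Adherence up to the rating is the better exposure measure for a Week 10 outcome, but no SAP statement is contradicted.
- **The fixed 84 is a further material error.** The ±2-day window at the end-of-treatment visit gives 82 to 86 dosing days, so full adherence reads 82/84 = 97.6% to 86/84 = 102.4%. No threshold is crossed.

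SAP 7.4.2.3 also refers to Section 6.4, which is not visible in the public text and could add detail. The formula in 7.3.2 is explicit all the same.

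**Conclusion.** The point holds as a minor one. For patients who complete treatment, 15.5% to 16.7% of the adherence denominator falls after the planned Day 71 rating, and roughly 12% to 19% across the Visit 8 window. Patients who stop between Visit 8 and the planned end are affected in part, because their days between rating and stop still count. Depending on dosing after the rating, pre-rating adherence from 52% to 72% can sit at the edge of the ≥60% group, and from 70% to 90% at the edge of the ≥75% group.

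This rests on daily dosing to Day 84, on on-site doses being credited, and on nothing in the unseen Section 6.4 limiting the score to doses before Visit 8. Selection on response through later dosing is possible, but its size is unknown. The primary conclusion is untouched.

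**What to change.** For the Adherent Set and the ≥60%, ≥75% and ≥90% subgroups of the Week 10 endpoint, compute AiCure adherence from Day 1 to the day before the Visit 8 ZAN-BPD rating, or to the last dose if earlier. Where there is no Visit 8 rating, use planned Day 71 in place of the rating day. The denominator is 4 times the patient's actual days in that interval. Keep the full-period score as a descriptive summary.

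The cost is a short SAP revision and a date cut on the AiCure dosing records. No visit, assessment or primary analysis changes. SAP 7.3.1 already calculates tablet-count compliance at Week 10, so a Week 10 cut fits existing practice.

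The SAP should also say what the change does not do. Adherence before Day 71 is still observed after randomisation and may respond to earlier symptoms. The subgroup comparisons therefore remain non-randomised and exploratory.
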